## 12. Anticipated Adverse Effects and Precautions for Use

### 12.1 Precautions for Use in Operating Environment

Do not use in locations exposed to moisture.

- Do not use the device with wet hands.
- Do not store the device in direct sunlight.
- Do not store near heating appliances.
- Avoid storing in areas with sudden humidity changes or poor ventilation.
- Do not store in locations where the device may be subjected to excessive impact or vibration.
- Use the device within an ambient temperature of 5–40°C and relative humidity of 5–95%.
- Consider ambient temperature and humidity during use, and keep the device away from dust, chemicals, and flammable substances.
- Do not disassemble or dismantle the device.

## 12.2 Precautions During Use

- Do not drop or subject the device to strong impacts.
- Do not measure blood pressure after smoking, drinking alcohol, exercising, bathing, eating, or consuming caffeine.
- Do not activate the device when it is not worn on the wrist.
- Dispose of the device, components, and accessories in accordance with local regulations to prevent environmental pollution.
- Check for any visible abnormalities on the blood pressure monitor.
- Inspect the charging cable for visible damage or abnormalities.

## 12.3 Anticipated Adverse Effects

- Using the device during an MRI scan may result in severe burns. Do not wear the device during MRI procedures. If this occurs during proper use, immediately remove the device from the patient.
- Avoid placing the blood pressure cuff over sites with arterial catheters or intravenous lines.
- Individuals with severe hematological disorders or blood conditions should use the device under a doctor's supervision. Temporary bruising or bleeding may occur due to cuff compression.

## 12.4 General Precautions

- Do not adjust medication dosage based on the measurement results.
- Take medications only as prescribed by a doctor. The diagnosis and treatment of hypertension can only be performed by a physician.
- Consult a doctor before using this device if you experience any of the following conditions:
- Arrhythmias such as atrial or ventricular extrasystoles or atrial fibrillation, arteriosclerosis, reduced arterial elasticity, diabetes, advanced age, pregnancy, preeclampsia (eclampsia or pre-eclampsia), or kidney disease.
- Movement, tremors, or chills during measurement may affect blood pressure readings.
- Do not use the device simultaneously with other electronic medical devices.
- Do not measure blood pressure on wrists that are injured or under treatment.
- If you experience pain or other unusual skin sensations while using the device, stop using it immediately and consult a doctor.

For more details, refer to Appendix 2\_H2-BP User Manual0-42\_Full Document.

### **13. Criteria on Termination and Early Suspension (Criteria on drop out in the middle and etc.)**

The test may be terminated or stopped in the middle for the patients falling on the following cases.

- When the subject withdrew the agreement for participation
- When the study is discontinued due to severe abnormal reaction or contingent accident
- When the subject does not visit and follow the procedures specified in the plan or at impossibility of those matters
- Difficulties on continuing the study due to the severe complication occurrence
- When the subject inappropriate to the selection criteria participated into the study
- When the subject falling on the exclusion criteria participated into the study
- When the blood pressure difference measure with the reference device is over the following error range
  - Entire data from the experimenters is excluded when any pair of the blood pressure data at the systolic area measured with the reference device is differed over 1.60kPa.
  - Entire data from the experimenters is excluded when any pair of the blood pressure data at the diastolic area measured with the reference device is differed over 1.07kPa.
- Other cases decided as disturbing the consistent study by the researcher-in-charge.

The experimenter is entitled to stopping the study freely when the experimenter withdraws the agreement for participating. The reasons and the data related to the clinical study shall be recorded and kept when the study is suspended.

### **14. Criteria, Methods, and Reporting for the Assessment of Safety, Including Adverse Events**

#### **14.1 Safety Evaluation Variables**

##### **1) Adverse Events (AEs)**

Any clinically significant medical condition or abnormality observed after the application of the blood pressure monitor will be recorded as an Adverse Event (AE). Clinically significant abnormalities identified during safety assessments, such as vital sign monitoring or physical examinations, will also be classified as AEs. If a clinically significant medical condition or abnormality confirmed before the application of the investigational device worsens after its application, it will be considered a new AE.

#### **14.2 Definitions of Adverse Events**

##### **1) Adverse Event (AE)**

An AE refers to any unintended sign (e.g., abnormal laboratory finding), symptom, or disease that occurs in a subject during the clinical trial, whether or not it is causally related to the investigational device.

##### **2) Adverse Device Effect (ADE)**

An ADE refers to any harmful and unintended reaction caused by the investigational device, for which a causal relationship with the device cannot be excluded.

### 3) Unexpected Adverse Device Effect

A Unexpected Adverse Device Effect is an ADE that differs in nature or severity from the information provided in the investigator's brochure, device labeling, or other available medical device documentation.

### 4) Serious Adverse Event/Serious Adverse Device Effect (Serious AE/ADE)

An SAE/SADE refers to an AE or ADE that meets any of the following criteria:

- (1) Results in death or poses a life-threatening risk
- (2) Requires hospitalization or prolongation of existing hospitalization
- (3) Results in permanent or significant disability or functional impairment
- (4) Causes a congenital anomaly or birth defect
- (5) Involves other medically significant conditions

For medically significant situations that are not explicitly listed but are deemed to have a serious impact on the subject's health and well-being, the determination of SAE will depend on the medical judgment of the investigator and relevant experts. Pre-planned hospitalizations or treatments, as well as hospitalizations for unchanged pre-existing conditions during the trial, will not be classified as SAEs.

#### 14.3 Safety Assessment Criteria and Methods

Consider the frequency and severity of adverse events described in the supporting documentation, together with any abnormal findings if other clinical tests are performed. Adverse events should be recorded and categorized according to the medical glossary for regulated adverse events and documented in the case record, including whether the event occurred, the name of the event, the date of occurrence, the outcome, the date of disappearance, whether it was a serious adverse event (SAE), the severity of the event, the causal relationship to the investigational device, the treatment involved, and whether it was treated.

##### 1) Severity of Adverse Events

The severity of AEs will be assessed using the following criteria:

- (1) Mild: Causes minimal discomfort that does not interfere with normal daily activities and is easily tolerated by the subject.
- (2) Moderate: Causes noticeable discomfort that significantly interferes with daily activities.
- (3) Severe: Causes discomfort that makes normal daily activities impossible.

Expected adverse reactions will also be classified as AEs, and their severity will be categorized as mild, moderate, or severe. Other adverse effects due to surgical interventions will be managed through medication or surgical treatment, and the investigator may decide to terminate the trial if necessary.

##### 2) Causal Relationship Between Adverse Events and the Investigational Device

- (1) Definitely related: The temporal relationship between the event and device use is plausible, and no other cause better explains the event. The AE resolves upon discontinuation of device use and reoccurs upon reapplication (if reapplication is feasible). Additionally, the AE is consistent with previously known information about the device.

- (2) Probably related: There is evidence of device use, the temporal relationship between device use and AE occurrence is plausible, reapplication is unnecessary, and the AE resolves upon discontinuation of the device.
- (3) Possibly related: There is evidence of device use, and the temporal relationship is plausible, but other potential causes cannot be ruled out. The AE resolves upon discontinuation of the device.
- (4) Possibly not related: There is evidence of device use, but a more probable alternative cause exists. The AE resolves upon discontinuation of the device, or the causality remains unclear. Additionally, if reapplication is performed (where feasible) and the AE does not recur, or the causality remains unclear, the event is considered possibly not related.
- (5) Definitely not related: The device was not used, or the temporal relationship between device use and AE occurrence is implausible, or a clear alternative cause is identified.
- (6) Unknown: Information is insufficient or conflicting, and further investigation is not feasible or cannot confirm causality.

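### All three related causality grades require the event to resolve once the device is stopped, so a fatal or permanent device injury cannot be graded as related

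*Combined protocol and SAP*

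**What the plan says.** Section 14.3 2) lists six grades. The three on the related side each carry a resolution clause:

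- *Definitely related*: "The AE resolves upon discontinuation of device use and reoccurs upon reapplication (if reapplication is feasible". The feasibility qualifier covers reapplication, not resolution.
- *Probably related*: "reapplication is unnecessary, and the AE resolves upon discontinuation of the device".
- *Possibly related*: "but other potential causes cannot be ruled out. The AE resolves upon discontinuation of the device".

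*Possibly not related* is the only grade that offers an alternative to resolution: "The AE resolves upon discontinuation of the device, or the causality remains unclear". It also needs a likelier cause other than the device. *Definitely not related* and *unknown* have no resolution clause.

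Elsewhere, section 14.2 2) defines an adverse device effect (ADE) as a harmful reaction "for which a causal relationship with the device cannot be excluded". Section 14.2 4) counts death among the outcomes that make an AE or ADE serious, and also this one: "Results in permanent or significant disability or functional impairment". Section 14.4 sends an event to the regulator when the investigator considers it serious, unexpected and potentially related. Within that route, fatal or life-threatening events have a 7-day deadline.

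**The concern.** Resolution on stopping is useful evidence about cause when an event can resolve. As a required element it fails for exactly the outcomes that matter most, because a death or a permanent impairment cannot resolve after any interval. The protocol foresees such outcomes as device effects and gives the fatal ones a reporting deadline, yet its own scale offers no related grade for them.

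The classification of the gravest events is at stake, and through it the regulator report. The criterion also separates device effects from other events poorly in this study: readings are brief and, under section 9, made on a single day, so the device comes off soon in every subject whatever the cause of an event.

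**Working it through.** No arithmetic applies. The check takes the six definitions as worded and asks which of them a given event can meet.

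**Event A: death or permanent impairment, plausible timing, no other cause found, information sufficient.**

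| Grade | Element that decides | Met? |
|---|---|---|
| 1 Definitely related | Resolution on stopping | No |
| 2 Probably related | Resolution on stopping | No |
| 3 Possibly related | Resolution on stopping | No |
| 4 Possibly not related | A likelier other cause | No |
| 5 Definitely not related | Device not used, implausible timing or a clear other cause | No |
| 6 Unknown | Too little or contradictory information | Not by its own definition |

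Result: 0 of 3 related grades and 0 of grades 1 to 5. *Unknown* is all that remains, although its own condition is not met.

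**Event B: as A, but the device is one of several possible causes and none is likelier.** This is the case that grade 3 appears to be written for, and it fails on the resolution sentence alone. Grades 4 and 5 fail for want of a likelier or clear other cause. *Unknown* is again what is left.

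**Event C: cuff bruising that fades over some days.** Section 12.3 anticipates this: "Temporary bruising or bleeding may occur due to cuff compression". If resolving upon discontinuation means gone when the device comes off, grades 1 to 3 are closed. If it means clearing at some time afterwards, the resolution clause is met. The text does not say which. The opening of section 14.3 asks for the date on which an event disappears, and section 14.3 3) follows events until they return to the state before the device was applied. Both favour the wider reading. Events A and B fail on either reading.

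**The sections side by side.**

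- Section 14.2 2) has no resolution element, so events A and B are ADEs there. Section 14.3 2) cannot grade either of them as related.
- Section 14.2 4) names death and permanent impairment as outcomes of a serious ADE. Section 14.3 2) leaves both without a related grade.
- Section 14.4 sets a 7-day deadline for fatal or life-threatening events judged potentially related. The only scale the protocol gives for that judgement cannot return a related grade for the fatal ones.
- No section states which of the six grades count as an ADE or as potentially related, so nothing elsewhere corrects the mismatch.

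**The case against.** The strongest reply concerns consequence. Section 14.4 requires every serious event to reach the monitor within 24 hours whatever its suspected cause, and the IRB under the site's procedures. The monitor then reports in writing to the sponsor within a further 24 hours, and the sponsor makes its own causality assessment. A reader might infer that fatal events would go unreported. The documents do not support that.

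A reader might also infer that regulator reports and ADE counts are bound to be biased. That too goes further than the text. The regulator trigger is what the investigator considers potentially related, not a numbered grade, and an event graded *unknown* could still be an ADE under section 14.2 2). Section 15 plans no analysis of ADEs, so no planned estimate is distorted.

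Nor does the text show that every lasting event, or every harm listed in section 12.3, is shut out of the related grades. Bruising is described there as temporary and can be read as resolving. Burns are mentioned only for wear during an MRI scan, which is not a study procedure. Anticipated bruising would also not ordinarily enter the regulator route, which opens with serious and unexpected events.

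These points limit the reach of the concern but do not remove the defect. The regulator trigger still rests on the investigator's view, the case report form records a causality judgement, and no other scale is provided to the investigator or the sponsor. Section 5.1 expects little additional risk from a non-invasive measurement, which makes a fatal or permanent device effect unlikely but does not make the rule right if one occurs.

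**Conclusion.** The point holds for fatal and permanent events. All three related grades carry a condition that such events cannot meet, and without a likelier other cause only *unknown* is left. This is a stated rule that misclassifies if followed, not a missing detail, and it conflicts with sections 14.2 2), 14.2 4) and 14.4. For events that persist and then fade, the wording is ambiguous and no more than that.

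The effect on reporting is possible rather than certain: a fatal or permanent device effect could be misclassified and kept out of the regulator route, while the monitor, the IRB and the sponsor would still hear of it. The accuracy endpoints, the sample size and the planned analyses are unaffected.

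The conclusion assumes that each element in a grade's definition must be met, which is how the text reads, and that investigators use this scale when judging relatedness, since no other is given. The documents give no rate for such events, so the number that might be affected cannot be estimated.

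**What to change.** In section 14.3 2), make resolution on stopping and recurrence on reapplication supporting evidence, to be weighed where assessable, and not a condition of grades 1 to 3. Let plausible timing and the presence or absence of other causes define the grades. This also removes the ambiguity over bruising.

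Then reconcile the scale with sections 14.2 2) and 14.4 by stating which grades count as an ADE and which as potentially related. Read literally, the ADE definition takes in every grade except *definitely not related*. Whether that should include *possibly not related*, where another cause is likelier, is a choice for the sponsor to make and write down.

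The cost is wording in the protocol and in the guidance for completing the case report form, with no change to design, sample size or analysis. The downside is that slightly more events may be classed as device effects.

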### **3) Treatment and progress**

During this clinical study, the principal investigator and personnel in charge shall ensure the safety of the subjects, and in the event of a serious adverse medical device event (SADE), prompt and appropriate measures shall be taken to minimize the adverse event, and the principal investigator may stop the trial in consultation with the sponsor. All adverse events occurring during the clinical study period, even if not related to the medical device, shall be recorded in detail in the case record, including symptoms and signs, onset/end date, severity, treatment and outcome, and relationship to the test device. In addition, the adverse event shall be observed, as far as possible, until the adverse event returns to the condition or baseline value prior to the application of the medical device, or until the principal investigator or responsible person can determine that the adverse event has normalized, or until further observation is deemed unnecessary.

#### **14.4 Safety Reporting Method**

The Principal Investigator (PI) shall educate the study personnel, subjects, and legally authorized representatives on all potential adverse events (AEs) that may occur following the use of the investigational device. Subjects shall also be instructed to report any events that occur post-use.

During the clinical study, the investigator must report all Serious Adverse Events (SAEs) and Serious Adverse Device Effects (SADEs) to the designated monitor within 24 hours of becoming aware of the event, regardless of their causal relationship with the investigational device. The investigator must also report the event to the Institutional Review Board (IRB) according to the safety reporting procedures of the clinical trial site. To protect subject confidentiality, the subject identification code shall be used instead of personal identifiers such as name, social security number, or address.

The designated monitor shall submit a written report to the sponsor within 24 hours of receiving the SAE/SADE report. The sponsor and IRB shall review the initial report, and if necessary, contact the investigator for further details. The sponsor will assess the causal relationship between the adverse event and the investigational device.

If the investigator considers the event to be serious, unexpected, and potentially related to the use of the investigational device, the event shall be documented as an Unexpected Serious Adverse Device Effect (USADE) and reported to the Ministry of Food and Drug Safety (MFDS) within the following timeframes:

- (1) Death or life-threatening events: Must be reported within 7 days of awareness, with a follow-up detailed report submitted within 8 days of the initial report.
- (2) All other serious or unexpected adverse device effects: Must be reported within 15 days of awareness.

Events that do not immediately threaten life, result in death, or require hospitalization but are deemed medically significant and necessitate immediate intervention based on medical judgment shall also be classified as SAEs.

For emergency room visits exceeding 24 hours, hospitalization criteria shall be met. However, the following situations shall not be classified as SAEs:

- (1) Emergency room visits lasting less than 24 hours
- (2) Pre-planned hospitalizations prior to investigational device application
- (3) Hospitalization for cosmetic surgery
- (4) Scheduled surgeries or procedures without adverse events
- (5) Planned hospitalizations or extended stays for pre-scheduled surgeries or examinations

## **15. Points to be Considered in Data Analysis and Statistics**

### **15.1 Statistical Analysis Methods**

#### **(a) Efficacy Analysis Population**

##### **A. Intention-To-Treat (ITT) Population**

All subjects who were randomly assigned for the clinical study must be included in the primary analysis. Complete follow-up of all randomized subjects is required.

##### **B. Full Analysis Set (FAS) Population**

This population adheres most closely and completely to the ITT principle. It includes subjects who provided informed consent, participated in the study, received the investigational device, and were assessed for the efficacy evaluation variables.

##### **C. Per Protocol (PP) Population**

This population consists of subjects from the FAS group who completed the trial without major protocol deviations. Major protocol deviations include violations of inclusion/exclusion criteria, missing efficacy evaluation variables, and other critical deviations. Subjects with significant protocol violations will be reviewed and determined in the analysis population adjudication meeting prior to analysis.

#### **(b) General Principles of Outcome Analysis**

The primary efficacy analysis is performed based on the PP population. For statistical hypothesis testing, a two-sided test is conducted with a significance level of 5%, and a two-sided 95% confidence interval is presented.

### (c) Handling of Missing Data

If missing data occur due to dropout or other reasons, no imputation is performed. Analyses will be conducted only on the collected data.

### (d) Handling of Outliers

Outliers are defined as cases where the subject's blood pressure remains inconsistent. Such cases will not be reflected in the efficacy evaluation. For criteria regarding inconsistent blood pressure, reference should be made to the exclusion criteria and dropout criteria.

## 15.2 Primary Endpoint

[figure not shown]
- (1) Average on difference between blood pressures measured with investigational device and comparator
- (2) Standard deviation on the blood pressures measured with investigational device and comparator. (Based on count of measurement)

## 15.3 Secondary Endpoint

- (1) Standard deviation on the blood pressures measured with investigational device and comparator. (Based on count of subjects)

## 15.4 Bland-Altman Analysis

For the data measured with H2-BP and stethoscope type blood pressure gauge, it is desirable to follow the analysis procedures suggested Bland and Altman(1986). Make the respective scatter plot on averages of blood pressure data at the systolic and diastolic area to compare by matching with the data from H2-BP and stethoscope type blood pressure gauge. (See the example of the scatter plot). Make respective plot for the systolic and diastolic area.

Average of data measured with H2-BP and stethoscope type blood pressure gauge

Example of scatter plot. N = 255, SD = Standard Deviation to check matching level between the data measured at systolic area with H2-BP and stethoscope type blood pressure gauge

“Average” on the above plot means the average of the data measured with H2-BP and stethoscope type blood pressure gauge at each point, and the “difference” is the one between data measured with H2-BP and stethoscope type blood pressure gauge at each point. The average should be known from each scatter plot and the horizontal line should be drawn to find  $\pm SD$  and  $\pm 2SD$ .

